Follow-up period	 Starts, for each individual, at randomization to one of the vaccination strategies (baseline) Ends at diagnosis of SARS-CoV-2 infection (i.e., outcome of interest), death, loss to follow-up, the date of receiving a booster dose, 168 days after baseline (24 weeks), or the end of the study period (March 1, 2022), whichever occurs first. 	 Sequential trial emulation: Starts, for each individual: Vaccine group: time of completing a primary vaccination schedule No (or partial) vaccine group: first eligible time (time of completing a primary vaccination schedule of the matched pair) Ends at diagnosis of SARS-CoV-2 infection, death (all causes), vaccination (for unvaccinated controls), completed primary vaccination of the matched control (for vaccinated persons), booster dose (for vaccinated persons), booster dose of the matched vaccinated persons), booster dose of the matched vaccinated person (for unvaccinated controls), or the end of the study period (i.e., the most recent date at which data is available at time of analysis). Loss to follow-up due to emigration or 'disenrollment' from the health care system not taken into account. Newly vaccinated individuals (completing a primary vaccination schedule) are eligible for inclusion in the "vaccine group" of the study, even if they had previously been selected in the "no vaccine group" (as controls).
Outcome	Laboratory-confirmed SARS-CoV-2 infection	A documented laboratory-confirmed SARS-CoV-2 infection, thus excluding self-reported test results
Causal contrast of interest	Per-protocol effect.	Observational analog of the per-protocol effect.

In the target trial (Figure 1), eligible participants are enrolled from January 1, 2021 (start of the SARS-CoV-2 vaccination campaign) until September 1, 2021 (start of the SARS-CoV-2 booster vaccination campaign). As such, the enrolment period in the target trial covers a

Funded by the European Union period of 9 months. For each eligible participant, follow-up starts at the moment of randomisation (baseline, t_0) and ends at diagnosis of SARS-CoV-2 infection (outcome of interest), death, loss to follow-up, receiving a booster dose, or 6 months after baseline. The period of data collection runs until March 1, 2022 to allow for a minimal follow-up period of 6 months for those participants with baseline (t_0) at the end of the enrollment period.

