In the sequential emulated target trial (Figure 2), each eligible individual is considered as a different individual at each eligible time (i.e., *daily*). As such, a sequence of nested (*daily*) trials are emulated with increasing time $(t_1, t_2, ..., t_n)$, iterating over the days in the enrollment period. At each eligible time during the enrollment period, the vaccination status of eligible individuals is assessed and every individual who has completed a primary vaccination schedule at that time (treated/exposed) is matched to an individual who has not (yet) completed the primary vaccination schedule (control). Newly vaccinated individuals (completing a primary vaccination schedule) are eligible for inclusion in the study, even if they had previously been selected in the "no (or partial) vaccine group". Follow-up ends at diagnosis of SARS-CoV-2 infection, death, death of matched person, completed primary vaccination (for unvaccinated or partially vaccinated controls), completed primary vaccination of the matched control (for primary vaccinated persons), booster dose (for primary vaccinated persons), booster dose of the matched vaccinated person (for unvaccinated or partially vaccinated controls), or the end of the study period. The study period ends at the most recent date at which data is available at the time of analysis. The data extraction period starts from the date of the first documented SARS-CoV-2 infection, in order to appropriately identify individuals with a previously documented SARS-CoV-2 infection.

[figure not shown]

Figure 1. Timeline of the target trial (ideal hypothetical trial).

BY-COVID is funded by the European Union's Horizon Europe research the European Union and innovation programme under grant agreement number 101046203.

[figure not shown]

Figure 2. Timeline of the sequential emulated target trial (actual study design reusing Real World Data).

BY-COVID is funded by the European Union's Horizon Europe research the European Union and innovation programme under grant agreement number 101046203.

Sources of information

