The analysis requires the secondary use of individual level data from COVID-19 registries (COVID-19 public health surveillance and monitoring information system of COVID-19 cases and SARS-CoV-2 vaccination population registry), insurance registry or health system users databases (*i.e., patient administrative information*) or data from Electronic Health Records (EHR, *i.e., comorbidities*), and death registration data. All data sources contain routinely collected data both from healthcare or public health information systems. For the variables required for the study, we refer to the common data model specification published in Zenodo (14).

A full join of the COVID-19 cases and SARS-CoV-2 vaccination records, linking all registries using unique pseudonyms at individual level, will be performed to obtain all people vaccinated with at least one dose of the SARS-CoV-2 vaccine (any of the available brands) in a resident area and/or with a documented positive diagnosis (irrespective of the type of test) for SARS-CoV-2 infection (COVID-19). In addition, linkage of patient administrative information and information on patient comorbidities is required to account for confounding factors (age, gender, comorbidities, immune status, foreign, pregnancy, residence area, essential worker, institutionalised) in the causal inference analysis. Data extraction is foreseen from the first date of a documented SARS-CoV-2 infection in the population until the most recent date at which data is available at the time of analysis. Park et al. (15) adopted a comparable approach to obtain data from the Korean COVID-19 vaccine effectiveness cohort, in their study comparing the effectiveness of two vaccines in preventing SARS-CoV-2 infection. They linked a registry with all COVID-19 laboratory-confirmed cases and a registry with SARS-CoV-2 vaccination data in South Korea.

Each country/region (Aragon (Spain), Belgium, Austria, Finland; Norway, Estonia and The Netherlands) will pull the data from their respective data sources conditional on data availability and access.

Participants

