For each person, follow-up ends at the occurrence of the outcome event (i.e., a confirmed SARS-CoV-2 infection), death (all causes), completing primary vaccination (for unvaccinated or partially vaccinated controls), completing primary vaccination of the matched control (for vaccinated persons), vaccination with a booster dose (for vaccinated persons), vaccination with a booster dose of the matched vaccinated person (for unvaccinated or partially vaccinated controls), or the end of the study period (i.e., the most

BY-COVID is funded by the European Union's Horizon Europe research the European Union and innovation programme under grant agreement number 101046203.

recent date at which data is available at time of analysis). Newly vaccinated persons (completing a primary vaccination schedule) are eligible for inclusion in the study, even if they have previously been selected as a control. As such, the matched controls enrolled at a particular day during the enrollment period are those who are unvaccinated (or partially vaccinated) at this date but may receive a first (or second) vaccination dose at a later date during the data extraction period.

Differences in the occurrence of a SARS-CoV-2 infection (as a time-to-event outcome) between primary vaccinated and unvaccinated or partially vaccinated individuals (average treatment effect, ATE (16)) will be computed by using adjusted Cox proportional-hazards models (17), and hazard ratios (HRs) and a robust variance estimate will be obtained.

A secondary analysis will be performed where the effectiveness of primary vaccination in preventing SARS-CoV-2 infection is assessed for different vaccine brands (e.g. BioNTech-Pfizer, Moderna, Johnson-Johnson, Astrazeneca, Novavax), hence conducting a stratified analysis using the matched pairs constructed for the primary analysis. Further, we can assess vaccine effectiveness during different time periods, with a dominant circulation of different SARS-CoV-2 variants.

Several sensitivity analyses will be performed accounting for different imputation algorithms, and different matching algorithms and compared in covariate balance after matching, robustness of the survival estimate and computing efficiency of the algorithm.

HRs and variance estimates will be collected from each country or region, and a meta-analysis will be performed in which the HRs are pooled by using the inverse variance method (18).

Ethical aspects

Balance risk/benefit

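### The emulation keeps people who emigrate or disenrol in the risk set, although the target trial ends their follow-up; the HR is biased to the extent that departed time differs between arms

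*Protocol*

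**What the plan says.** In the target trial column of Table 1 (Follow-up period), loss to follow-up is a listed end: "Ends at diagnosis of SARS-CoV-2 infection (i.e., outcome of interest), death, loss to follow-up, the date of receiving a booster dose". The same cell adds a limit of 168 days after baseline and a study end of March 1, 2022.

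The emulation column says the opposite about departure: "Loss to follow-up due to emigration or 'disenrollment' from the health care system not taken into account". The narrative under Target Trial specification and emulation begins its list of ends with "Follow-up ends at diagnosis of SARS-CoV-2 infection, death, death of matched person, completed primary vaccination (for unvaccinated or partially vaccinated controls" and continues through completion by the matched control, boosters and the end of the study period. Departure is not in it, nor in the list in the Statistical analysis plan section. None of the emulation's lists carries the 168-day limit; instead, "The study period ends at the most recent date at which data is available at the time of analysis".

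The planned sensitivity analyses concern imputation and matching algorithms only. Under Sources of information the study draws on "insurance registry or health system users databases" for patient administrative information, without saying whether these hold a date of departure.

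**The concern.** The outcome is a documented laboratory-confirmed infection. Once a person has left, the site can record no infection, no dose and no booster for that person. The record therefore contributes event-free time and cannot itself trigger the endings that normally close a pair: completion by the control or a booster in the vaccinated member. It stays open until the partner or the end of data closes it, and without a 168-day limit that can take years.

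Departed time lowers the observed rate in the arm where it accumulates. If it accumulates equally, it nearly cancels in the HR. If not, the HR moves. The HRs are then pooled across up to seven countries or regions. The analysis is population-wide, so sampling error is likely to be small, and a distortion of several percent that varies with local mobility could matter.

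**Working it through.** The protocol states no departure rate, infection rate or assumed HR, so there is no figure of its own to reproduce. All rates below are assumptions.

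**Step 1: size when departure differs between arms.** If only one arm loses people at annual rate d over T years, the average departed fraction is about d × T / 2. The HR is then multiplied by about 1 − dT/2 (vaccinated leave) or 1 + dT/2 (controls leave).

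- 168 days: T = 168/365.25 = 0.460. With d = 0.10, dT/2 = 0.023, giving factors of about 0.977 and 1.023.
- 424 days (1 January 2021 to 1 March 2022): T = 1.161. With d = 0.10, dT/2 = 0.058, giving about 0.942 and 1.058.

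Solving the expected Cox score equation (control hazard 0.15 per year, true HR 0.5) gives:

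| Follow-up | Vaccinated leave, 2 / 5 / 10% per year | Controls leave, 2 / 5 / 10% per year | Equal departure, 1–10% per year (true HR 0.2 or 0.5) |
|---|---|---|---|
| 168 days | 0.995 / 0.989 / 0.977 | 1.005 / 1.012 / 1.023 | 1.000 |
| 424 days | 0.988 / 0.971 / 0.944 | 1.012 / 1.030 / 1.061 | at most 1.003 |
| 3 years | 0.970 / 0.927 / 0.862 | 1.033 / 1.084 / 1.172 | at most 1.017 |

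Entries are HR with departure ignored divided by true HR. Censoring at departure returns the true HR, provided departure is independent of infection risk given the matching variables.

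If a fraction g of controls has already left when matched, the factor is about 1/(1 − g). For g = 0.05 this is 1.053 (score equation at 168 days: 1.055).

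**Step 2: does the plan itself create a difference?** Table 1 excludes people with neither a dose nor a positive diagnosis.

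- A never-dosed control who leaves before a positive test never enters the data. A vaccinated person who leaves stays in, event-free. This puts departed time on the vaccinated side and lowers the HR.
- A person with one dose of a two-dose schedule who leaves stays in the data and can remain in the control pool. This raises the HR.

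The two pull in opposite directions, and the documents give no numbers to weigh them.

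**Step 3: size under the plan's entry rule.** Simulation of 600,000 pairs with pair-wise ending. Assumptions: 30% of controls never vaccinated, the rest completing after a mean of 58 days; 70% of vaccinees boosted at days 150 to 240; control hazard 0.0008 per day; true HR 0.4. Where two runs are shown, they are separate runs of the same set-up.

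| Population, departure per year | Follow-up | HR ignored / censored | Ratio | VE points |
|---|---|---|---|---|
| Entry rule, 2% both arms | 900 days | 0.171 / 0.178; 0.169 / 0.176 | 0.961; 0.960 | 0.7; 0.7 |
| Entry rule, 5% both arms | 900 days | 0.162 / 0.178; 0.165 / 0.183 | 0.910; 0.902 | 1.6; 1.8 |
| Entry rule, 2% both arms | 168 days | 0.273 / 0.274 | 0.996 | 0.1 |
| Entry rule, 5% both arms | 168 days | 0.278 / 0.281 | 0.989 | 0.3 |
| All residents, 5% both arms | 900 days | 0.396 / 0.398 | 0.995 | 0.2 |

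VE points are 100 × the difference between the two HRs. The set-up has no partially vaccinated leavers held in the control pool, so it shows only the downward pull in Step 2.

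In the entry-rule rows at 900 days the censored HR is still about 0.178 against a true 0.400, a gap of 0.222. Ignoring departure adds only 0.007 to 0.018.

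**The case against.** The deviation is declared, in the table whose purpose is to show where the emulation differs from the ideal trial. A reader might take it for a hidden contradiction; it is not. But disclosing a rule does not remove its effect, and no sensitivity analysis addresses it.

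Matching on age, residence area, foreign status, essential work and institutionalisation probably removes part of any difference in emigration between arms. That stands, and it is why equal departure is the fairer base case. The residual asymmetry in the entry-rule rows comes from who is allowed into the data, not from unequal departure.

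Three stronger readings are tempting and not supported:

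- **That effectiveness is overstated.** This follows only if the entry rule dominates; partially vaccinated leavers work the other way, so the net sign is open.
- **That about 3 points of effectiveness are at stake.** Such a figure arises (0.431 against 0.400 at 900 days) in an all-resident population with 2% per year departing among vaccinees and 10% among controls. That is not this plan's population, and nothing in the documents supports a fivefold contrast after matching.
- **That the departure date is already available.** The protocol names alternative registries, subject to availability at each site, and does not list such a date.

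It is also fair that the size depends on two other features, the entry rule and the missing 168-day limit. They are separate issues and should not be counted again here.

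**Conclusion.** The point holds in a conditional and modest form. The emulation departs from its own target trial by keeping people at risk when no event can be recorded. The bias depends on how far departed person-time differs between arms, and its direction cannot be fixed from the documents.

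With assumed departure of 2 to 5% per year and the plan's entry rule, the effect is about 4 to 10% of the HR at 900 days and about 1% or less at 168 days. It is near zero with equal departure and all residents. Most of the HR error in the entry-rule scenarios comes from the entry rule itself, and censoring at departure does not repair that. Added heterogeneity between countries is plausible but was not quantified. This is a cheap improvement, not a fatal flaw.

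**What to change.** Replace the sentence in the emulation column of Table 1 with a rule of this kind: *where the linked insurance or health-system-user registry holds a date of emigration or disenrolment, follow-up of both members of a pair ends on the date either one leaves.* Add the same event to the lists in the narrative on the emulated trial and in the Statistical analysis plan section. It follows that a person whose departure date has passed is not drawn as a control.

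Sites without the date should say so and keep the present sentence as a stated limitation. They should be separated from the other sites in a sensitivity pooling, which should also show the result with follow-up limited to the target trial's 168 days. That limit can be applied at every site and, in the scenarios above, removes most of the effect.

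The cost is one more date field in the common data model, some lost person-time, and the likelihood that some sites cannot supply the date. Ending follow-up at departure also assumes that leaving is unrelated to infection risk given the matching variables, which should be stated.

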Eligibility criteria	 Study population: All individuals eligible to be vaccinated. Enrollment period: From the start of the SARS-CoV-2 vaccination campaign (January 1, 2021) to the start of the SARS-CoV-2 booster vaccination campaign (September 1, 2021). Age: 5 to 115 years old, included (all individuals eligible to be vaccinated). Previous infection: Individuals without a SARS-CoV-2 infection before enrolment. Country: Individuals living in the respective country 	 Study population: All individuals vaccinated with at least one dose of the SARS-CoV-2 vaccine (any of the available brands) and all individuals eligible to be vaccinated with a documented positive diagnosis (irrespective of the type of test) for SARS-CoV-2 infection during the data extraction period. Enrollment period: From the start of the SARS-CoV-2 vaccination campaign (January 1, 2021) until the start of the SARS-CoV-2 booster vaccination campaign (September 1, 2021). Age: 5 to 115 years old, included (all individuals eligible to be vaccinated). Previous infection: Individuals without a documented confirmed infection before completing the primary vaccination schedule (i.e. enrolment) or before January 1, 2021 (SARS-CoV-2 vaccine roll-out) for those not having completed a primary vaccination schedule (controls). Country: Resident of the registered individuals in the COVID-19 cases and vaccination datasets. Individuals with neither a registered vaccine dose nor a positive diagnosis during the data extraction period are therefore excluded.
Treatment strategies	 Primary analysis Completing a primary vaccination schedule (from any vaccine brand) Not completing a primary vaccination schedule (either not receiving a vaccine or being only partially vaccinated). Secondary analysis Completing a homogeneous primary vaccination schedule with 	Same as in Target Trial Specification. Vaccination status ascertainment (including brand, dose and date) based on the vaccination registry. Date of being primary vaccinated (completing a primary vaccination schedule) is considered as 14 days after receiving the final dose of the primary vaccination schedule (one dose for the Johnson-Johnson vaccine and two doses of any of the other vaccines considered).

Table 1. Protocol of the target randomised control trial and target trial emulation by using observational data.

Funded by

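### The emulation drops the target trial's 168-day and 1 March 2022 limits without a reason, so no common follow-up horizon is fixed before the site hazard ratios are pooled

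*Protocol*

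**What the plan says.** In the Protocol, Table 1, row on the follow-up period, the target-trial column closes its list of stopping events with "168 days after baseline (24 weeks), or the end of the study period (March 1, 2022), whichever occurs first". The text below the table explains the calendar date: "The period of data collection runs until March 1, 2022 to allow for a minimal follow-up period of 6 months" for those enrolled last. That text gives the per-person limit as 6 months, not 168 days.

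The emulation column of the same row has its own complete list: infection, death, vaccination of the control, booster of the vaccinated person, the matching pair-censoring rules, and finally "the end of the study period (i.e., the most recent date at which data is available at time of analysis". The paragraph on the sequential emulated trial repeats this and states "The study period ends at the most recent date at which data is available at the time of analysis". The follow-up paragraph of the section Statistical analysis plan uses the same open end. Neither 168 days nor 1 March 2022 appears in any of the three places.

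The section Sources of information ends data extraction at the same open date and has each country or region pull its own data as access allows. The objectives set out two sequential stages, with two sites and then seven. The Statistical analysis plan section fits a Cox model per site and pools the HRs by inverse variance.

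**The concern.** The horizon is part of the causal contrast. A per-protocol effect over 24 weeks and one over all available follow-up are different quantities, and the two columns of Table 1 describe one each. The departure is unexplained, and the data do not force it, because infection and vaccination dates come from registries.

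The end date is also not prespecified. It moves with the date of analysis and may differ between sites. If effectiveness varies with time since vaccination or with the circulating variant, a single Cox HR averages over whatever follow-up a site happens to have. Sites with different cut dates would then contribute averages over different horizons to one pooled figure.

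**Working it through.** **Inputs from the Protocol.** Campaign and enrolment start 1 January 2021. Enrolment ends 1 September 2021. Target-trial end 1 March 2022. Limit 168 days. Time zero is 14 days after the final dose (Table 1, treatment strategies). Project end 30 September 2024 (Chronogram), used only as an outer bound for the data cut.

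**The plan's own figures.** 24 × 7 = 168 days. From 1 September 2021 to 1 March 2022 is 30 + 31 + 30 + 31 + 31 + 28 = 181 days, or 6 calendar months. Both reproduce. Since 181 > 168, every pair with time zero by 1 September 2021 can complete 168 days. If 1 September were instead read as the date of the last dose, time zero would be 15 September and 181 − 14 = 167 days would remain, one day short.

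**Longest follow-up as the emulation is written.**
- 1 January 2021 to 30 September 2024 is 3 × 365 + 273 = 1,368 days. The earliest time zero is 14 days later, so the maximum is 1,354 days; 1,354 / 168 = 8.1.
- From 1 September 2021 it is 1,368 − 243 = 1,125 days if time zero itself is that day (1,125 / 168 = 6.7), or 1,111 days if the last dose was given that day (1,111 / 168 = 6.6).
- With an assumed cut at 31 December 2022, the earliest time zero gives 729 − 14 = 715 days.
- The 1 March 2022 date alone would still allow 424 − 14 = 410 days, so the two limits are not interchangeable.

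**What limits follow-up in practice.** Both members of a pair stop when the control completes vaccination and at "booster dose (for primary vaccinated persons), booster dose of the matched vaccinated person (for unvaccinated or partially vaccinated controls". Long follow-up is confined to pairs in which neither happens, and the Protocol gives no rate for either.

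**Illustration (all inputs assumed).** True HR 0.1 at time zero, rising linearly to 1 at 365 days; control hazard 0.0005 per day; exponential pair censoring. The constant HR that solves the Cox score equation is:

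| Pair-censoring half-life | 168 days | 1,125 days | 1,368 days |
|---|---|---|---|
| 30 days | 0.20 | 0.20 | 0.20 |
| 90 days | 0.26 | 0.39 | 0.39 |
| 180 days | 0.28 | 0.55 | 0.55 |
| none | 0.31 | 0.82 | 0.85 |

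The attainable maximum of 1,354 days lies between the last two columns. With slower waning (HR 1 reached at 730 days) and no censoring, 168 versus 1,368 days gives 0.20 versus 0.71. With no waning, the HR is 0.10 at every horizon.

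**The case against.** The best defence is that the open end is disclosed and used consistently, in a table that deliberately separates an ideal trial from the study actually done. Figure 2, the emulation timeline, is also not available here. This does not meet the point. The emulation column says where it matches the target trial for treatment strategies, but for follow-up it gives a different list. No reason is offered, and nothing in the data requires it. A cap shown only in a figure would contradict the text in three places.

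The objections to size and direction do stand. A reader might infer that every country will estimate a different, waning-diluted HR. That needs cut dates that differ and an effect that changes with time, and the Protocol gives neither cut dates nor a waning rate. It mentions periods of dominant variants, as an optional analysis, but not waning. Heavy censoring at booster or control vaccination can make the shift negligible.

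Nor does it follow that the pooled HR is meaningless. Inverse-variance pooling of unlike effects still gives a weighted average, though one that is hard to interpret. A further inference, that late follow-up loses events to self-testing, has no support: the Protocol only excludes self-reported results from the outcome.

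**Conclusion.** The point holds in a limited form. The emulation departs from its own target trial in both the per-person limit and the calendar end, gives no reason, and fixes no common horizon before pooling. That rests on the text alone.

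The consequence for the estimate is conditional. Possible follow-up of about 1,111 to 1,354 days, against 168, assumes data to the project's last day and pairs that nothing else censors. The HR shift in the illustration runs from none to large and rests on assumed waning, hazard and censoring. A dilution of the effect is tempting to infer but is not shown. Waning would push the HR towards 1. However, people with no dose enter the data only through a positive test within the extraction window (Table 1, eligibility; Participants), so longer follow-up can count more of those qualifying tests as control events, which pushes the other way. The net direction is not established.

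Because the contradiction concerns the primary estimand and is cheap to remove, it should be resolved before any site result is pooled.

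**What to change.** - In the emulation column of Table 1, the paragraph on the sequential emulated trial and the follow-up paragraph of the Statistical analysis plan section, add 168 days after time zero as a stopping rule and replace the open end with 1 March 2022, at every site.
- In Sources of information, set one common end date for the extraction window. Cohort entry depends on that window as well, so capping follow-up alone would leave site-dependent selection. A common date makes the window's end the same everywhere; it does not remove the selection itself.
- Use one unit, 168 days or 6 months, throughout, and state that the enrolment end refers to time zero, so that 181 days remain after the last entry.
- Put later data in a labelled secondary analysis by time since vaccination.

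The cost is a few changes of wording and one censoring line in the shared pipeline. The downside is fewer late events, which the specified target trial does not count. If the open end is intended, the Protocol should instead give the reason, revise the target-trial column to match, and still fix one cut date for all sites.

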Randomization is mimicked by matching on all confounding factors required to ensure comparability (conditional exchangeability) of the groups defined by vaccination (as identified in the Directed Acyclic Graph, see causal model specification published in Zenodo (13)). For each day during the enrollment period (i.e., sequential emulated trial), all newly vaccinated individuals (i.e. those having completed the primary vaccination schedule) will be matched in a 1:1 ratio to unvaccinated (or partially vaccinated) controls based on the variables listed in the adjustment set to close non-causal backdoor paths and so, eliminate confounding bias (16): age, gender, residence area, pregnancy, being an essential worker, being institutionalised, being a foreigner, presence of comorbidities, and the immune status. Presence of comorbidities is defined as having one of the following conditions: diabetes, obesity, health failure, COPD, a solid tumour without metastasis, chronic kidney disease, sickle cell disease, chronic liver disease, and hypertension (see the data model specification published in Zenodo (13) for variable-level specification, including data dictionaries and crosswalks defining each variable using several international disease *classification systems*). Immune status is defined as having one of the following conditions: HIV infection. blood cancer, transplantation, primary immunodeficiency, immunosuppression (see the data model specification published in Zenodo (13) for variable-level specification and crosswalks).

The matching will be performed using exact matching (whenever possible) or distance based algorithms such as nearest neighbour matching based on the Mahalanobis distance based on the probability of intervention (vaccination) for those individuals not matched using exact matching. Covariate balance after matching will be evaluated considering mean differences between variable values (standardised for continuous variables) between vaccinated and unvaccinated groups, with a difference of 0.1 or less considered to be acceptable.

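### The 0.1 balance limit is applied to yes/no covariates as a raw difference, so one present in 10% or less of both matched groups passes however unbalanced it is

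*Protocol*

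**What the plan says.** The Statistical analysis plan section of the protocol mimics randomisation by 1:1 matching on "age, gender, residence area, pregnancy, being an essential worker, being institutionalised, being a foreigner, presence of comorbidities, and the immune status". At least six of these are presence/absence variables: pregnancy, essential-worker status, institutionalisation, foreigner status, comorbidity and immune status. The definitions support this reading; for example, "Immune status is defined as having one of the following conditions". Age is the only clearly continuous member of the set.

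Matching uses "exact matching (whenever possible) or distance based algorithms such as nearest neighbour matching based on the Mahalanobis distance", the distance step serving people whom exact matching could not place.

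The check on the result compares the covariate means of the two groups, and the differences are "standardised for continuous variables) between vaccinated and unvaccinated groups, with a difference of 0.1 or less considered to be acceptable". No other numerical balance criterion is given. The same section later names covariate balance among the criteria for comparing matching algorithms in the sensitivity analyses.

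The effect "will be computed by using adjusted Cox proportional-hazards models (17), and hazard ratios (HRs) and a robust variance estimate will be obtained". That sentence does not list the adjustment covariates.

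**The concern.** One number is used on two scales. For age, 0.1 means a tenth of a standard deviation. For a yes/no covariate it means 10 percentage points, whatever the prevalence. The rarer the covariate, the weaker the test, and below a certain prevalence it cannot fail at all.

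This matters because matching is how the study seeks conditional exchangeability, and this rule is the protocol's only numerical criterion for whether it was achieved. A rare characteristic that is related both to vaccination timing and to infection risk could be clearly unbalanced and still be reported as acceptable. A comparison of matching algorithms on the same raw metric would be equally insensitive to it.

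This is a stated decision rule, not a detail left to a separate analysis plan, so it can be judged as written.

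**Working it through.** **Inputs.** From the protocol: the limit of 0.1, standardisation for continuous variables only, and the list of covariates. The protocol gives no covariate prevalences and no covariate–infection associations, so all of those below are assumptions, shown over a range. There is no derived figure in the plan to reproduce.

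**Step 1: when the rule cannot fail.** Let p1 and p0 be the covariate's prevalence in the vaccinated and control groups. The raw difference satisfies |p1 − p0| ≤ max(p1, p0). If both are 10% or less, the raw difference is at most 0.10 and the rule passes. A failure needs a prevalence above 10% in at least one group; 12% versus 1% (raw 0.11) does fail.

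**Step 2: what passes, on the standardised scale.** SMD = (p1 − p0) / √{[p1(1 − p1) + p0(1 − p0)] / 2}.

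For 10% versus 1%: 0.09 / √[(0.0900 + 0.0099)/2] = 0.09 / 0.2235 = 0.40.

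| Assumed prevalences | Raw difference | Rule as written | SMD |
|---|---|---|---|
| 3% vs 1% | 0.02 | pass | 0.14 |
| 5% vs 2% | 0.03 | pass | 0.16 |
| 10% vs 1% | 0.09 | pass | 0.40 |
| 10% vs 0% | 0.10 | pass | 0.47 |
| 55% vs 45% | 0.10 | pass | 0.20 |
| 12% vs 1% | 0.11 | fail | 0.46 |

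Common covariates are also treated leniently, as the 55% versus 45% row shows.

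**Step 3: what 0.1 would allow if binary covariates were standardised too.** Solving SMD = 0.1 for the raw gap at a given mean prevalence:

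| Mean prevalence | 1% | 2% | 5% | 10% | 20% | 50% |
|---|---|---|---|---|---|---|
| Largest raw gap | 0.010 | 0.014 | 0.022 | 0.030 | 0.040 | 0.050 |

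The rule as written allows a raw gap of 0.10 at any prevalence.

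**Step 4: possible effect on the HR.** If the imbalance existed and the model did not adjust for the covariate, an approximate distortion factor is [1 + p1(R − 1)] / [1 + p0(R − 1)], where R is the assumed hazard ratio of the covariate for infection.

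| Imbalance | R = 2 | R = 3 | R = 5 |
|---|---|---|---|
| 5% vs 2% | 1.05/1.02 = 1.03 | 1.10/1.04 = 1.06 | 1.20/1.08 = 1.11 |
| 10% vs 1% | 1.10/1.01 = 1.09 | 1.20/1.02 = 1.18 | 1.40/1.04 = 1.35 |

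With the groups reversed, the factors are the reciprocals.

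**Step 5: where an imbalance would have to come from.** Exactly matched pairs contribute zero difference. If a share s of all pairs is distance-matched, the overall difference is s times the difference within that share. With s = 20% (assumption), an overall gap of 9 points needs a gap of 0.09/0.20 = 45 points among the distance-matched pairs. With s = 10%, even complete imbalance in those pairs gives 0.10 overall and passes.

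**The case against.** The strongest reply is that a lenient diagnostic is not a biased estimate. Exact matching comes first and leaves no imbalance on the matched variables, so the 10% versus 1% case is near the extreme: it needs a net 9% of all pairs to be discordant in the same direction, all from the distance-matched remainder. The more moderate 5% versus 2% case moves the HR by only 3% to 6% for a covariate hazard ratio of 2 to 3. The Cox model is described as adjusted, and the sensitivity analyses examine whether the survival estimate is robust to the choice of matching algorithm. All of this stands, and it limits the consequence. It does not repair the criterion, because the adjustment covariates are not named in that sentence and the dilution in step 5 also makes an all-pairs check insensitive in the pairs that most need it.

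A reader might infer more than the protocol supports:

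- **That institutionalisation and immune status can never fail the check, or that they are strong confounders.** The first holds only at 10% or less in both groups. The protocol states neither their prevalence nor their strength of association.
- **That the distance step uses vaccination probability alone and has no caliper.** The wording, "nearest neighbour matching based on the Mahalanobis distance based on the probability of intervention (vaccination) for those individuals not matched using exact matching", is unclear and is introduced as an example. The protocol says nothing about a caliper, and that is commonly settled in an analysis plan.
- **That balance will be examined only over all pairs together.** The text compares vaccinated with unvaccinated groups and does not say whether results are also split by matching step.

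**Conclusion.** The point holds as a defect in the balance criterion. For yes/no covariates the 0.1 limit is a raw 10 percentage points, and any such covariate at 10% or less in both matched groups passes even under complete imbalance. That part is algebra and needs no assumption. Whether it applies to a particular covariate depends on prevalences that the protocol does not give.

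The HR distortions, 1.03 to 1.11 for 5% versus 2% and 1.09 to 1.35 for 10% versus 1%, are conditional on three things: the assumed prevalences, an assumed covariate hazard ratio of 2 to 5, and a Cox model that omits the covariate. They show what the rule could let through and do not predict the study's result. The documents do not show that imbalance will occur. The change should be made because the rule is the only numerical balance criterion and is easily corrected.

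**What to change.** Apply the 0.1 limit to the standardised mean difference of every covariate, including binary ones and each level of categorical ones. Show raw prevalences by group alongside. This helps for very rare covariates, where even 0.5% versus 0% only just reaches an SMD of 0.1. Report balance separately for distance-matched pairs. State that any covariate above the limit enters the adjusted Cox model.

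The cost is a changed phrase and a few more lines of output. Some covariates that the current rule accepts may be flagged.

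No redesign of the matching follows from this point. A caliper, compulsory exact matching on chosen variables, or dropping vaccinees without a close control would be separate design choices. Dropping vaccinees would also depart from the stated plan to match every newly vaccinated person and would change the population to which the effect refers.
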